5. STUDY INTERVENTIONS AND CONCOMITANT MEDICATIONS

5.1. Randomization

5.1.1. Randomization

Participants will be assigned a screening number in the IRT system at the time of consent.

Randomization and Day 1 visits must not occur until participant eligibility has been confirmed. Once eligibility has been confirmed, the investigator or designee will randomize the participant using the IRT system. Once a participant number has been assigned to a participant, it will not be reassigned to any other participants. The participant number assignment and randomization may be performed up to 3 days prior to Day 1 visit provided all screening procedures have been completed and participant eligibility criteria has been confirmed.

Participants who meet eligibility criteria will be randomized in a 2:1 ratio to Treatment Groups 1 and 3.

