1.2.4. Clinical Studies of Lenacapavir With GS-5423 and GS-2872

GS-US-536-5816 is a randomized, blinded, POC Phase 1b study to evaluate the safety and efficacy of a single dose each of a long-acting regimen of LEN, GS-5423, and GS-2872 in adults with HIV-1 infection who are virologically suppressed (HIV-1 RNA < 50 copies/mL) on oral ART.

The primary cohort included eligible adults with HIV-1, no history of virologic failure (VF) or ARV drug resistance, a CD4+ T-cells nadir ≥ 350 cells/ μ L, screening CD4+ T-cells count > 500 and on first-line ART for at least 2 years with demonstrated virologic suppression (HIV-1 RNA < 50 copies/mL) for at least 18 months who had sensitivity to both GS-5423 and GS-2872, as measured by the PhenoSense monoclonal antibody assay (Monogram Biosciences), were randomized in a 1:1 ratio to 2 treatment groups.

All participants received GS-5423 (30 mg/kg intravenous [IV]) and oral LEN 600 mg Day 1 and Day 2 and LEN for subcutaneous (SC) injection 927 mg on Day 1. The 2 randomization arms differed only in the dose of GS-2872 that they received (10 mg/kg or 30 mg/kg administered IV).

Participants discontinued their background oral ARV regimen 1 day prior to receiving study drugs on Day 1. At Week 26, all participants who remained virologically suppressed, resumed their background oral ARV baseline regimen (or compatible regimen selected by the investigator) and return to the clinic for visits at Weeks 38 and 52.

Twenty-one participants were enrolled into the primary cohort and randomized, 20 received the complete study drugs (10 in each treatment group), one participant received oral LEN and withdrew consent prior to completing dosing procedures. The median age of participants was 44 years (range: 25 to 61 years), 18 (86%) were male sex at birth; and at baseline, all had HIV-1 RNA < 50 copies/mL and CD4 count ≥ 500 cells/ μ L.

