- 11) Estimated glomerular filtration rate (eGFR) ≥ 30 mL/min according to the Modification of Diet in Renal Disease formula {[Lacombe 2008](#), [Levey 2006](#)}.
- 12) All of the following laboratory results at Screening Visit 2:
 - A) Alanine aminotransferase (ALT) and aspartate aminotransferase (AST) $\leq 5 \times$ upper limit of normal (ULN).
 - B) Total bilirubin ≤ 1.5 mg/dL, or normal direct bilirubin.
 - C) Absolute neutrophil count $\geq 750/\text{mm}^3$; (chronic neutropenia with no clinical significance can enroll at investigator discretion).
 - D) Platelets $\geq 50,000/\text{mm}^3$; and hemoglobin ≥ 8.5 g/dL.
- 13) Participants assigned female at birth of childbearing potential (as defined in [Appendix 11.3](#)) must have a negative serum pregnancy test at Screening Visit 2 and negative urine pregnancy test at Day 1 prior to study drug administration.
- 14) Participants assigned female at birth of childbearing potential who engage in heterosexual intercourse must agree to utilize protocol-specified method(s) of contraception as described in [Appendix 11.3](#).

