5.1.2. Blinding

Blinding of treatment assignments or data will not be performed in this study.

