6.3.10. Patient-Reported Outcomes

Patient-reported outcome questionnaires (if available) will be completed by participants in both treatment groups at the visits specified in [Table 1](#), and [Table 2](#), and include HIV-dependent quality of life (HIVDQoL), the HIV Treatment Satisfaction Questionnaire status version (HIVTSQs), HIV Treatment Satisfaction Questionnaire change version (HIVTSQc), and the HIV Treatment Preference Questionnaire (HIVTPQ).

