3.1.2. Full Analysis Set

The Full Analysis Set (FAS) includes all randomized participants who have received at least one dose of the complete long acting study drug regimen (ie, SC LEN + GS-5423 and GS-2872) or continued with their baseline ART regimen. For the FAS, all efficacy data will be included, unless specified otherwise. This is the primary analysis set for efficacy analyses.

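### Full Analysis Set exclusion for incomplete dosing falls almost entirely on Group 1, and no all-randomised efficacy analysis shows its effect

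*Protocol*

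**What the plan says.** **Analysis sets.** Under SAP 3.1.2 a randomised participant enters the FAS having "received at least one dose of the complete long acting study drug regimen", which the SAP spells out as SC LEN plus both antibodies, or by carrying on with baseline ART. Protocol 8.3.1.1 has the same two routes. Participants are analysed in the arm to which they were randomised (SAP 3.2). SAP 3.1.1 defines an All Randomized Analysis Set but makes it primary only for listings. The secondary efficacy sets are Per Protocol sets cut from the FAS (SAP 3.1.3). The missing = failure, missing = excluded and subgroup analyses also use the FAS (SAP 6.3.2.1, 6.3.3).

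**Timing of randomisation.** Protocol 5.1.1 opens with "Randomization and Day 1 visits must not occur until participant eligibility has been confirmed". It then says "The participant number assignment and randomization may be performed up to 3 days prior to Day 1 visit", on the condition "provided all screening procedures have been completed and participant eligibility criteria has been confirmed". Protocol 5.1.2 adds: "Blinding of treatment assignments or data will not be performed in this study". For participants of childbearing potential, Inclusion Criterion 13 requires a "negative urine pregnancy test at Day 1 prior to study drug administration".

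**Questionnaires.** Protocol 6.3.10 says that these "will be completed by participants in both treatment groups at the visits specified in" Tables 1 and 2. The treatment preference, treatment satisfaction (status version) and quality of life forms are first given at Day 1 (Protocol Table 2; SAP Tables 13-1 and 13-2). Neither document sets their order relative to randomisation.

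**The concern.** The two arms face different hurdles to be counted. Group 1 must get through an injection visit and two infusions; Group 3 need only keep taking its pills. A Group 1 participant who learns the arm and withdraws, or who starts dosing and stops, drops out of every efficacy denominator. On the < 50 copies/mL endpoint that person would otherwise count as a non-success. The sample size section gives Phase 3 planning as the purpose of the estimate, and for that purpose failure to deliver the regimen is information worth keeping.

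Two smaller matters arise at the same point in the trial. For some participants, eligibility cannot be fully confirmed before Day 1, yet randomisation may come earlier. And answers on treatment satisfaction or preference may be given after the participant knows whether the regimen will change.

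**Working it through.** **1. The plan's own figures.** Inputs: 50 and 25 participants, 2-sided 95% CI, exact unconditional method (Protocol 8.11). Using the score statistic and 0.025 per side:
- 8/50 against 0/25 gives p = 0.0239; 7/50 gives 0.0403. The threshold is 8, as stated.
- 12/50 against 1/25 gives p = 0.0239; 11/50 gives 0.0403. The threshold is 12, as stated.
- Chance of at least one AE of 5% incidence: 1 − 0.95^50 = 92.3% and 1 − 0.95^25 = 72.3%, as stated.

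**2. Planning figures after exclusions from Group 1 only (assumed 1 to 5).** The threshold becomes 8 or 9 failures with none in Group 3, and 11 to 13 with one. The AE probability for Group 1 falls to between 91.9% and 90.1%. These are small changes; comparability of the arms is the real issue.

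**3. A possible exclusion rate.** The documents give none for this trial. The only precedent is Phase 1b (Protocol 1.2.4), where of 21 randomised "one participant received oral LEN and withdrew consent prior to completing dosing procedures", and efficacy was reported on 10 + 10 = 20. That is 1/21 = 4.8%, exact 95% CI 0.1% to 23.8%. Applied to 50: 50 × 1/21 = 2.4, with a range from 50 × 0.001 = 0.05 to 50 × 0.238 = 11.9. One event in 21 settles little, so a range is shown.

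**4. Effect on the endpoints.** Let k of the 50 be excluded.
- Secondary, all others suppressed: FAS (50 − k)/(50 − k); all randomised (50 − k)/50.
- Primary, one failure among those dosed: FAS 1/(50 − k); all randomised 1/50.

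| k (assumed) | < 50, FAS | < 50, all randomised | ≥ 50, FAS | ≥ 50, all randomised |
|---|---|---|---|---|
| 0 | 50/50 = 100% | 50/50 = 100% | 1/50 = 2.0% | 1/50 = 2.0% |
| 1 | 49/49 = 100% | 49/50 = 98% | 1/49 = 2.0% | 1/50 = 2.0% |
| 2 | 48/48 = 100% | 48/50 = 96% | 1/48 = 2.1% | 1/50 = 2.0% |
| 5 | 45/45 = 100% | 45/50 = 90% | 1/45 = 2.2% | 1/50 = 2.0% |
| 12 | 38/38 = 100% | 38/50 = 76% | 1/38 = 2.6% | 1/50 = 2.0% |

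For k = 2 the exact 95% CIs of the secondary proportion are 92.6% to 100% and 86.3% to 99.5%. Complete suppression is a simplification: Protocol 1.4.1.2 reports 1 failure in Group 1 at Week 26 and 3 at Week 52. With 3 failures and k = 2, the proportions are 45/48 = 93.8% and 45/50 = 90.0%, a gap of similar size.

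**5. Protocol 5.1.1 beside Criterion 13.** Section 5.1.1 makes confirmed eligibility a condition of early randomisation. Criterion 13 includes a test done at Day 1. For participants of childbearing potential the condition cannot be fully met before Day 1. The documents do not give their share of the trial.

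**The case against.** **Disclosure.** SAP 3.1 tabulates exclusions from each analysis set with reasons, by treatment group, and SAP 4.1 counts participants randomised but never treated. A reader could rebuild the denominators. That stands, and it limits the harm. But counts are not estimates, and the never-treated line would miss someone who took only oral LEN, who belongs to the Safety Analysis Set and not to the FAS.

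**Wording of the FAS.** The definition does not tie each route to an arm, so a Group 1 participant who stayed on pills might be argued in. The on-treatment rule in SAP 6 counts Group 1 data from the last complete long-acting dose, which presupposes that each Group 1 member had one. The arm-by-arm reading is the natural one.

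**The 3-day window.** A reader might infer that it makes losses before Day 1 fall only on Group 1. The documents do not support that. The Day 1 pregnancy test is scheduled in both arms, and a disappointed Group 3 participant can also withdraw. The asymmetry comes from the FAS definition. The Phase 1b loss occurred after dosing had begun, so randomising at Day 1 would not have prevented it.

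**Questionnaires.** A reader might also infer that all baselines are answered knowing the arm and are biased in opposite directions. Early randomisation is optional, the schedules place randomisation at Day 1, and nothing shows how many were randomised earlier or which way answers would shift. The window is not the only route either, since the order within Day 1 is open. Protocol 8.10 offers only an optional descriptive summary, and the readable SAP has no questionnaire analysis.

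**Conclusion.** The point holds as a minor one. FAS exclusion for incomplete dosing falls almost entirely on Group 1, and no planned efficacy analysis shows what that does to the estimates. The primary proportion and the planning thresholds change little. The secondary < 50 copies/mL proportion could be overstated by about 4 percentage points if 2 of 50 are excluded, by nothing if none are, and by more at the upper end of the Phase 1b interval. All of this rests on an assumed exclusion rate, because the documents do not say how many randomised participants lacked a complete dose.

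The tension between Protocol 5.1.1 and Criterion 13 is real but confined to participants of childbearing potential. For the questionnaires, the documents support only that baseline answers can follow knowledge of the arm.

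**What to change.** In SAP 6.1.3 and 6.2.2, add supportive snapshot tables for Weeks 26 and 52 on the All Randomized Analysis Set, by randomised arm, for both the ≥ 50 and < 50 copies/mL proportions. State that a randomised participant with no complete dose and no on-treatment HIV-1 RNA is classed as No Virologic Data and not as < 50 copies/mL. The rule has to be written down because the Group 1 on-treatment period is undefined without a complete dose. Protocol 1.4.1.2 already reports Week 52 results, so label these tables as supportive and added after results were known. If nobody was excluded they will match the FAS tables, and one sentence can replace them. The cost is one repeated set of tables.

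Reconcile Protocol 5.1.1 with Inclusion Criterion 13 so that the point at which eligibility counts as confirmed is clear for participants of childbearing potential.

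If the questionnaires are reported, state whether the Day 1 answers preceded randomisation. Collecting them before the arm is disclosed can help only future enrolment, at the price of less notice for Day 1 drug preparation; it cannot change anything for participants already randomised.

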5.1.2. Blinding

Blinding of treatment assignments or data will not be performed in this study.

5.2. Description and Handling of Lenacapavir, GS-5423, and GS-2872

5.2.1. Formulation

5.2.1.1. Lenacapavir

Lenacapavir tablets, 300 mg, are capsule-shaped, film-coated beige tablets, debossed with “GSI” on one side of the tablet and “62L” on the other side of the tablet. Each tablet core contains the equivalent of 300 mg LEN free acid in the form of LEN sodium salt. In addition to the active ingredient, LEN tablets, 300 mg, contain the following inactive ingredients: microcrystalline cellulose, mannitol, poloxamer 407, copovidone, croscarmellose sodium, magnesium stearate, polyethylene glycol, polyvinyl alcohol, talc, titanium dioxide, iron oxide red, iron oxide black, and iron oxide yellow.

Lenacapavir injection, 309 mg/mL, is a clear, yellow to brown solution for SC injection. In addition to the active ingredient (LEN sodium), LEN injection, 309 mg/mL, contains the following inactive ingredients: polyethylene glycol 300 and water for injection.

5.2.1.2. GS-5423

GS-5423 solution for infusion, 150 mg/mL, 1 mL/vial, or 2 mL/vial drug product will be supplied as a sterile, preservative-free, colorless to brownish yellow solution for IV administration. The drug product is composed of 150 mg/mL GS-5423 in histidine, acetate, trehalose, methionine, and polysorbate 20.

5.2.1.3. GS-2872

GS-2872 solution for infusion, 150 mg/mL, 1 mL/vial, or 2 mL/vial drug product will be supplied as a sterile, preservative-free, colorless to brownish yellow solution for IV administration. The drug product is composed of 150 mg/mL GS-2872 in histidine, acetate, trehalose, methionine, and polysorbate 20.

5.2.2. Packaging and Labeling

5.2.2.1. Lenacapavir

Lenacapavir tablets, 300 mg, are packaged in white, high-density polyethylene bottles. Each bottle contains either 4 or 5 tablets, silica gel desiccant, and polyester packing material. Each bottle is enclosed with a white, continuous thread, child-resistant polypropylene screw cap fitted with an induction-sealed, and aluminum-faced liner.

Lenacapavir injection, 309 mg/mL, is supplied as a sterile solution packaged in a single-use clear vial fitted with a rubber stopper and an aluminum flip-off seal.

5.2.2.2. GS-5423

GS-5423 solution for infusion, 150 mg/mL, 1 mL/vial, or 2 mL/vial drug product is supplied as single-use 2R, Type I clear glass vials, with coated elastomeric stoppers, capped with polypropylene flip-off caps with aluminum overseals.

5.2.2.3. GS-2872

GS-2872 solution for infusion, 150 mg/mL, 1 mL/vial, or 2 mL/vial drug product is supplied as single-use 2R, Type I clear glass vials, with coated elastomeric stoppers, capped with polypropylene flip-off caps with aluminum overseals.

Study drugs to be distributed to centers in the US shall be labeled to meet applicable requirements of the US FDA and/or other local regulations.

5.2.3. Storage and Handling

Until administration and dispensation to the participants, all study drugs should be stored in a securely locked area, accessible only to authorized site personnel. To ensure the stability and proper identification, study drugs should not be stored in a container other than the container in which they were supplied. Consideration should be given to handling, preparation, and disposal through measures that minimize drug contact with the body. Appropriate precautions should be followed to avoid direct eye contact or exposure when handling.

5.2.3.1. Lenacapavir

Lenacapavir tablets, 300 mg, should be stored below 30 °C (86 °F). Storage conditions are specified on the study drug label.

Lenacapavir injection, 309 mg/mL should be stored below 30 °C (86 °F) and protected from light. Storage conditions are specified on the study drug label.

5.2.3.2. GS-5423

GS-5423 solution for infusion, 150 mg/mL, 1 mL/vial, or 2 mL/vial drug product, should be stored at 2 °C to 8 °C and protected from light. Storage conditions are specified on the study drug label.

5.2.3.3. GS-2872

GS-2872 solution for infusion, 150 mg/mL, 1 mL/vial, or 2 mL/vial drug product, should be stored at 2 °C to 8 °C and protected from light. Storage conditions are specified on the study drug label.

5.3. Dosage and Administration

Treatment Group 1

Dose and administration of LEN, GS-5423, and GS-2872 for Treatment Group 1 are described below and in [Table 4](#).

Day 1:

Participants will receive the following study drugs. All study drugs should be administered on the same day (ie, no visit window is permitted for Day 1 study drug administration).

- Oral LEN 600 mg will be administered orally with approximately 240 mL water, without regard to food.
- SC LEN 927 mg will be administered within 30 minutes after oral LEN, as 2 SC injections at separate injection sites in the abdomen, within 15 minutes.
- GS-5423 2550 mg IV infusion will be administered immediately following (up to 1 hour after) the last SC LEN injection. Infusions of GS-5423 will be administered over 30 minutes.
- GS-2872 2550 mg IV infusion will be administered at least 15 minutes following (up to 1 hour after) the completion of GS-5423 IV infusion. Infusions of GS-2872 will be administered over 30 minutes.

Participants will discontinue their baseline oral ART following administration of the complete study drugs on Day 1.

Day 2:

Participants will self-administer oral LEN 600 mg at home with approximately 240 mL water, without regard to food, at approximately the same time as the oral LEN dose for loading on Day 1.

Weeks 26 and 52:

Virologic suppression (HIV-1 RNA < 50 copies/mL) from the preceding visit must be confirmed prior to proceeding with dosing visits.

Infusions of GS-5423 and GS-2872 will be sequentially administered following SC LEN injection:

- LEN 927 mg, as 2 SC injections at separate injection sites in the abdomen, within 15 minutes
- GS-5423 IV infusion of 2550 mg
- GS-2872 IV infusion of 2550 mg

Every 26 Weeks During the Extension Phase:

At each dosing visit during the extension phase, the following study drugs will be administered:

- LEN 927 mg, as 2 SC injections at separate injection sites in the abdomen, within 15 minutes
- Infusions of GS-5423 and GS-2872 can either be coadministered (preferred option) or administered sequentially (investigator discretion) following SC LEN injection:

— Coadministration

- GS-5423 2550 mg CCI
GS-2872 2550 mg CCI
IV infusion CCI

— Sequential administration

- GS-5423 2550 mg CCI [REDACTED]
[REDACTED] Infusions of GS-5423 will be administered over 30 minutes.
- GS-2872 2550 mg CCI [REDACTED]
[REDACTED] Infusions of GS-2872 will be administered over 30 minutes.

Table 4. Treatment Group 1 Treatment Table

Study Day	Treatment Group 1
Day 1	LEN 600 mg (two 300-mg tablets, PO) LEN 927 mg (two 1.5-mL injections, SC) GS-5423-2550 mg (IV infusion) GS-2872-2550 mg (IV infusion)
Day 2	LEN 600 mg (two 300-mg tablets, PO)
Weeks 26 and 52	LEN 927 mg (two 1.5-mL injections, SC) GS-5423-2550 mg (IV infusion) GS-2872-2550 mg (IV infusion)
Every 26 weeks during the extension phase	LEN 927 mg (two 1.5-mL injections, SC) GS-5423-2550 mg CCI [REDACTED] GS-2872-2550 mg CCI [REDACTED]

IV = intravenous; LEN = lenacapavir; PO = orally; SC = subcutaneous

Treatment Group 3

Day 1 Through Week 52:

Participants in Treatment Group 3 will stay on their baseline oral ART through Week 52.

Week 52:

Participants in Treatment Group 3 who are eligible and elect to participate in the extension phase will receive the study drugs of LEN, GS-5423, and GS-2872 as described below and in [Table 5](#).

Participants will receive the following study drugs. All study drugs should be administered on the same day (ie, no visit window is permitted for Week 52 study drug administration):

- Oral LEN 600 mg will be administered orally with approximately 240 mL water, without regard to food.
- SC LEN 927 mg will be administered within 30 minutes after oral LEN for loading, as 2 SC injections at separate injection sites in the abdomen, within 15 minutes.
- Infusions of GS-5423 and GS-2872 will either be coadministered (preferred option) or administered sequentially (at investigator discretion) following SC LEN injection:

— Coadministration

- GS-5423 2550 mg and GS-2872 2550 mg CCI

Infusions of GS-5423 and GS-2872 will be administered over 60 minutes.

— Sequential administration

- GS-5423 2550 mg CCI

Infusions of GS-5423 will be administered over 30 minutes.

- GS-2872 2550 mg CCI

Infusions of GS-2872 will be administered over 30 minutes.

Participants will discontinue their baseline oral ART following administration of the complete study drugs on Week 52.

Week 52 + 1 Day:

Participants will self-administer oral LEN 600 mg at home with approximately 240 mL water, without regard to food, at approximately the same time as the oral LEN dose on Week 52.

Every 26 Weeks During the Extension Phase:

At each dosing visit during the extension phase, the following study drugs will be administered:

- LEN 927 mg, as 2 SC injections at separate injection sites in the abdomen, within 15 minutes
- Infusions of GS-5423 and GS-2872 will either be coadministered (preferred option) or sequentially administered (investigator discretion) following SC LEN injection

— Coadministration

- GS-5423 2550 mg CCI [REDACTED]
[REDACTED] GS-2872 2550 mg CCI [REDACTED]
CCI [REDACTED]

— Sequential administration

- GS-5423 2550 mg CCI [REDACTED]
[REDACTED] Infusions of GS-5423 will be administered
over 30 minutes.
- GS-2872 2550 mg CCI [REDACTED]
[REDACTED] Infusions of GS-2872
will be administered over 30 minutes.

Table 5. Treatment Group 3 Treatment Table

Study Day	Treatment Group 3
Day 1 through Week 52	Continue background regimen
Week 52 ^a	LEN 600 mg (two 300-mg tablets, PO) LEN 927 mg (two 1.5-mL injections, SC) GS-5423 2550 mg (IV infusion) GS-2872 2550 mg (IV infusion)
Week 52 + 1 Day (at home)	LEN 600 mg (two 300-mg tablets, PO)
Every 26 weeks during extension phase	LEN 927 mg (two 1.5-mL injections, SC) GS-5423 2550 mg CCI [REDACTED] GS-2872 2550 mg CCI [REDACTED]

IV = intravenous; LEN = lenacapavir; PO = orally; SC = subcutaneous

a Participants in Treatment Group 3 who are eligible and elect to participate in the extension phase will receive LEN, GS-5423 and GS-2872.

